1. PROTOCOL SUMMARY

1.1. Synopsis

Title: A prospective case series evaluating a fibrillar collagen powder dressing to treat chronic, stalled lower-extremity wounds

Study Description: Chronic wounds are a source of significant morbidity and escalating healthcare costs. The wound care professional has a myriad of modern wound dressings to choose from when treating a wound, each of which has benefits and drawbacks. An understanding of how a given dressing performs in healing a particular wound is crucial in order to determine a clinical mapping of wound dressings to wound types; such a categorization would lead to more efficient clinical decision making and better patient outcomes. This case series will evaluate the ability of a fibrillar collagen powder to improve healing of chronic, stalled, lower-extremity wounds.

Objectives: Evaluate the ability of a fibrillar collagen powder dressing to treat chronic, stalled, lower-extremity wounds

Endpoints: **Primary:** Change in wound size over twelve week period
Secondary: 1) Change in Bates-Jensen Wound Assessment Tool score, 2) Change in reported pain level.

Study Population: Twenty adult patients with chronic lower-extremity wounds (i.e. below the knee) of greater than four weeks that have failed to respond to at least one advanced wound dressing treatment. Specific wound types include: pressure ulcers, diabetic ulcers, and venous leg ulcers.

Phase: Post-Market

Description of Sites/Facilities Outpatient podiatry clinics in the United States
Enrolling Participants:

Description of Study Intervention: Patients who meet the inclusion criteria will be provided with fibrillar collagen powder dressing (Puracol® Ultra Powder by Medline Industries, Inc.). The powder dressing will be used in

accordance with its label. After cleansing the wound by the clinical site staff, the powder is placed directly on the wound, and then the wound will be covered with an appropriate moisture retentive secondary dressing. Patients will visit the clinic twice a week to have the powder re-applied. Wound evaluations will take place once a week at the outpatient clinic, with the intervention lasting up to twelve weeks. Concurrent standard of care, such as compression for venous ulcers, will be provided.

Study Duration: Total time for study completion to allow accrual of all subjects, and appropriate treatment as per the protocol, will be approximately 12-18 months

Participant Duration: Participant duration in the study will be a maximum of twelve weeks. In the event a participant's wound completely heals prior to the end of twelve weeks, his or her participation in the study will be complete at the time of complete wound healing.

1.2. Schedule of Activities (SOA)

REQUIRED ASSESSMENTS	PRE-SCREENING Day -1	SCREENING VISIT Day 0 (May be combined with Initial Visit, Day 1)	INITIAL VISIT Day 1	DRESSING CHANGE VISITS Twice weekly (Every 3 days ± 1 day)	WOUND ASSESSMENT VISITS Once per week Every 7 days ± 2 days (May be combined with Dressing Change Visit)	FINAL VISIT 12 weeks from Initial Visit ³
Pre-Screening Questionnaire ¹	X					
Informed Consent		X				
Screening Form to assess eligibility		X				
Decision on eligibility		X				
Demographics			X			
Wound History			X			
Wound Photograph			X		X	X
Bates-Jensen Wound Assessment			X		X	X
Application of Puracol® Ultra			X	X	X ²	
Pain Assessment for dressing change			X		X	X
Secondary Dressing Notation			X	X	X ²	
Adverse Event Assessment		X	X	X	X	X

1: For participants contacting the research facility, 2: If combined with Dressing change visit, 3: Final visit may occur earlier in the event the participant's wound has completely healed before 12 weeks

2. INTRODUCTION

2.1. Background & Rationale

Chronic wounds, defined as damage to epidermal or dermal structures present for greater than four weeks without significant clinical improvement, in spite of appropriate clinical management, represent a substantial burden on the healthcare system. Costs for venous leg ulcers, a wound type that often becomes chronic, were estimated at \$3 billion annually as of 2006.¹ Other wound types, such as pressure ulcers and diabetic ulcers can also turn into chronic wounds, adding to healthcare costs and negatively impacting quality of life. These types of wounds frequently occur in the lower extremities due to venous or arterial insufficiency and pressure exerted on the foot or leg.

A key factor in wound healing is the production, deposition, and integration of collagen in the wound bed. Collagen is the most abundant protein in the human body, and it plays a key role in all phases of wound healing.² In chronic wounds, the deposition of *de novo* collagen is delayed and/or altered.^{3,4} In these wounds there is both a reduction of collagen deposition, coupled with increased breakdown of the collagen that does get deposited, that prevents it from integrating into the wound bed and healing the wound.

In an effort to augment the formation and integration of collagen into the wound bed, healthcare professionals often turn to collagen based dressings. These dressings are composed of bovine, porcine, or avian collagen; the dressings are often in the form of a sheet that can be applied directly to the wound or a powder that is sprinkled over the wound. The influx of collagen aids in addressing the microenvironment of the wound, which may provide a different mechanism of action for healing compared to other advanced wound treatments, which often address the macro environment (e.g. moisture retentive dressings). Due to this, collagen dressings may be particularly useful for chronic wounds that have not responded to other advanced wound treatments, such as silver sulfadiazine, calcium alginate, or hydrocolloid dressings. Indeed, a case series of twenty patients with chronic, stalled wounds demonstrated the ability of a bovine-based collagen dressing to advance the healing of these wounds.² In the current study, a novel, porcine-based powder dressing will be evaluated in order to determine if it can achieve similar ends.

2.2. Investigational Product

Puracol® Ultra Powder collagen wound dressing is a powder-like fibrillar collagen microsponge composed of Type I porcine dermis collagen. The dressing is a currently marketed, cleared device in the United States, indicated for the management of full and partial thickness wounds, including: pressure ulcers, diabetic ulcers caused by mixed vascular origin, venous ulcers, and several other wound types. Appendix 11.1.1 provides the label and instructions for use (IFU) for the device.

As Puracol® Ultra comes in powder form, a secondary dressing applied over the wound is necessary. An appropriate sized dressing from the Optifoam® Gentle silicone border series by Medline Industries Inc., will be applied. Information pertaining to these dressings is provided in Appendix 11.1.2. Furthermore, given that the standard of care for patients with venous ulcers entails

Fibrillar dressing for treating chronic, stalled wounds

MED-2018-DIV71-008

23 August 2018

V 1.0

CONFIDENTIAL

application of a compression dressing, patients with these types of wounds will also receive CoFlex® TLC Two-Layer Compression System dressing; this dressing is currently marketed for the management of venous ulcers. More information regarding the CoFlex® TLC Two-Layer Compression System dressing is available in Appendix 11.1.3.

2.3. Risk/Benefit Profile

2.3.1. Potential Study Risks

Participants may experience irritation or a reddening due to the dressing. Participants will be under the care of a healthcare professional while using the dressing, and he or she will be able to intervene appropriately if the dressing causes any irritation or reddening.

2.3.2. Potential Study Benefits

Participants may experience a healing of their chronic, stalled wound as a result of the study product application.

2.3.3. Assessment of Potential Risk/Benefit Profile

The study product will be used in accordance with its currently marketed IFU, and the risks to participants are minor. Participants may experience healing of their wound through the application of the dressing. Due to this, the risk/benefit profile is favorable.

3. OBJECTIVES AND ENDPOINTS

OBJECTIVES	ENDPOINTS	JUSTIFICATION FOR ENDPOINTS
Evaluate the ability of a fibrillar collagen powder dressing to treat chronic, stalled, lower-extremity wounds.	
Primary
 
Change in wound size 
Secondary
 
Change in BWAT scoreChange in reported pain level
General pain levelPain level at dressing change	
A reduction in wound size is indicative of healing 
The BWAT is a validated tool for wound healingPain is indicative of healing and wound status

4. STUDY DESIGN

4.1. Overall Design

This is a prospective, open-label, case series investigating if a currently marketed collagen dressing can result in improved healing of chronic, stalled, lower-extremity wounds. An outpatient podiatry clinic will enroll twenty patients with qualifying wounds and monitor wound healing progress over the course of twelve weeks.

4.2. End of Study Definition

The conclusion of the study for an individual participant will occur at their last Wound Assessment Visit, which will be after twelve weeks of participation or when the wound is completely healed, whichever comes first. The study will be deemed complete upon issuance of the final Clinical Study Report.

5. STUDY POPULATION

5.1. Inclusion Criteria

In order to participate in the study, a participant must meet *ALL* of the following criteria:

- Age 18+
- Has one of the following types of wounds below the knee:
 - Diabetic ulcers
 - Pressure ulcers
 - Venous ulcers
 - Ulcers of mixed-vascular origin
 - Traumatic wounds
 - Post-surgical wounds
- Wound has been present for at least four weeks
- Wound is free of necrotic tissue or debridement practices will take place prior to initial visit in order to remove necrotic tissue.
- Wound has not responded to at least one type of advanced wound care treatment
- Wound size is between 1 and 100 cm²
- Patient has adequate circulation as demonstrated by biphasic or triphasic Doppler waveform, measured within three months prior to study enrollment. If monophasic on exam, then non-invasive tests must display Ankle Brachial Index greater than 0.8 and no worse than mild disease on segmental pressures.
- Wound is confirmed as being free of infection and absence of osteomyelitis.

5.2. Exclusion Criteria

A participant must not meet *ANY* of the criteria below to participate in the study

- Pregnant, planning to become pregnant during the study timeframe, or breast feeding
- Unable or unwilling to receive porcine collagen

- Wound is infected or presence of osteomyelitis
- Allergy or sensitivity to collagen
- Inability, in the opinion of the Investigator to follow protocol requirements, attend follow up visits in a timely manner, or otherwise comply with the requirements of the protocol

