5.3. Strategies for Recruitment and Retention

The Principal Investigator (PI) maintains an outpatient podiatry clinic. The PI and/or site staff will offer enrollment to patients that may meet the inclusion/exclusion criteria. Participants will be provided with reminder notifications and documentation detailing their scheduled visits to the site.

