8. STATISTICAL CONSIDERATIONS

8.1. Sample Size Determination

As this is an open-label, observational case series, meant to evaluate clinical use of the study product, a formal power analysis was not conducted. Rather, a sample of 20 participants was chosen to provide an initial estimate of product performance in a clinical setting. Data from this study may be used to perform a power analysis for larger, future trial.

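### Entry rules do not ask whether the index wound is already on a collagen dressing or recently had another active therapy, so for some participants Day 1 may not be a pre-treatment baseline

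*Combined protocol and SAP*

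**What the plan says.** The only rule on earlier treatment is in Section 5.1: "Wound has not responded to at least one type of advanced wound care treatment". It does not name a kind of treatment, say how recent the treatment must be, or define non-response. The exclusions in Section 5.2 touch on collagen twice, once for allergy or sensitivity and once as "Unable or unwilling to receive porcine collagen". Neither concerns past or current use.

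The forms add no restriction. Pre-Screening Form 11.2.1 asks whether an advanced therapy has been tried. Item 9 of Screening Form 11.2.2 asks whether one was tried without success and has it listed as free text.

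The product can be obtained outside the study: Section 2.2 states "The dressing is a currently marketed, cleared device in the United States". Recruitment is from the investigator's outpatient podiatry clinic, where, under Section 5.3, "The PI and/or site staff will offer enrollment to patients that may meet the inclusion/exclusion criteria". The Schedule of Activities lets screening and the Initial Visit fall on the same day, and Section 6.3.2 makes the Day 1 photograph the baseline area. Section 8.3.1 then compares the Initial with the Final Visit, with no control group.

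**The concern.** A wound that failed an alginate some time ago and was later switched to this powder, or to another collagen dressing, meets every listed criterion while that treatment is under way. So does a wound that received some other active therapy shortly before Day 1. In the first case the study records a later stretch of treatment, not the response to starting it. In the second, part of the recorded change may belong to the earlier therapy.

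A control group would share such effects; this series has none. The result is also meant to be used: Section 8.1 says "a sample of 20 participants was chosen to provide an initial estimate of product performance in a clinical setting" and adds that the data may support a power calculation for a larger trial. If the mean change and its SD mix wounds starting the product with wounds already on collagen, later planning inherits that mixture.

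The background in Section 2.1 points to a particular setting, saying that "collagen dressings may be particularly useful for chronic wounds that have not responded to other advanced wound treatments". A wound already improving on collagen, or one that has already failed it, says little about that idea.

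**Working it through.** The plan has no figure to reproduce: Section 8.1 states that "a formal power analysis was not conducted" and gives no effect size or SD. The check is therefore a reading of the entry path, followed by arithmetic on stated assumptions.

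**1. Entry path for a wound now on collagen after an earlier failed treatment**

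| Step | What is asked | Does it stop this wound? |
|---|---|---|
| Form 11.2.1 | Has an advanced therapy been tried? | No |
| Section 5.1; Form 11.2.2 item 9 | Has one failed? | No, the earlier one did |
| Section 5.2; Form 11.2.2 items 1 and 4 | Collagen sensitivity; acceptance of a porcine product | No |
| Schedule of Activities | Run-in or earlier area measurement | None required |
| Initial Visit CRF 11.3.1 | Prior treatments and their duration | No; recorded after eligibility is decided, without a last-use date |

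**2. Direction.** Assume, for illustration only, a wound of 10 cm² when collagen began, 6 cm² on Day 1 and 2 cm² at week 12.
- Recorded change: 6 − 2 = 4 cm².
- Change since collagen began: 10 − 2 = 8 cm², over more than twelve weeks. The record omits the first 4 cm², so it understates the total response.
- Suppose instead that the therapy before Day 1 was something else, and that k of the recorded 4 cm² would have happened anyway. The record then overstates the product's contribution by k, anywhere from 0 to 4 cm².
- A wound already failing on collagen would pull the mean change down.

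One set of measurements can therefore mislead in either direction, depending on facts that the entry forms do not collect.

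**3. Size.** Each participant carries 1/20 = 5% of the mean. If a share f of wounds is affected and each is displaced by c SDs of wound-size change (either sign), the mean shifts by f × c. Neither f nor c is in the documents. Over an assumed range:

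| f (wounds of 20) | c = ±0.5 SD | c = ±1.0 SD |
|---|---|---|
| 10% (2) | ±0.05 | ±0.10 |
| 25% (5) | ±0.125 | ±0.25 |
| 50% (10) | ±0.25 | ±0.50 |

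For scale, the half-width of the 95% confidence interval in 8.3.1 is t(0.975, 19)/√20 = 2.093/4.472 = 0.47 SD. If only 15 were evaluable (an assumption), it would be 2.145/3.873 = 0.55 SD. Only the extreme corner of the table exceeds the half-width at n = 20. The shift, however, does not shrink with sample size, and the interval does not reflect it.

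**The case against.** The strongest reply is that this is a small, open, descriptive series. Section 4.1 says "This is a prospective, open-label, case series investigating if a currently marketed collagen dressing can result in improved healing", the tests are labelled exploratory, and the lack of a control already bars firm attribution of any before-after change. At f = 10% the shift is at most 0.10 SD over the assumed range. All of this stands, and it limits how much weight the point can bear.

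A second reply is that the title and objective speak of stalled wounds, and that Section 2.1 defines chronic wounds as ones that have not improved meaningfully under proper care. A wound shrinking on its current dressing would not fit. That is the evident intent, but Section 5.1 does not make it an entry test, and having failed one earlier treatment does not show that the wound is stalled on Day 1.

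A reader might also infer more than the documents support:
- **That the gap inflates the apparent effect by a known amount.** The direction is open, and no input for the size is given. The planned endpoint is also change in cm², so a percentage-point bias would be on a scale that the plan does not use.
- **That prior treatment plays no part in entry or analysis.** Item 9 requires a failed therapy. Prior treatments are collected under Section 6.3.1, and 8.3.1 permits modelling on baseline data, though optionally and without naming them.
- **That the clinic already uses the product.** The documents say only that it is marketed.
- **That the rationale restricts entry to wounds never treated with collagen.** Section 2.1 is worded as a possibility, and the objective sets no such limit.
- **That a four-week washout follows from Section 5.1.** That figure is wound duration and gives no basis for a washout.

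**Conclusion.** The omission is real. The entry rules admit wounds for which Day 1 falls during collagen treatment or soon after another active therapy, and for those wounds the Initial-to-Final change is not the effect of starting the product. How many there would be, and how far and in which direction they would move the mean, cannot be worked out from the documents; the table of shifts rests wholly on assumed f and c. This does not invalidate a descriptive series. It makes the baseline, and the estimate offered for planning a later trial, harder to interpret than necessary, and it can be put right cheaply.

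**What to change.** 1. **Section 5.2 and Form 11.2.2:** add an exclusion, with a matching question, for index wounds being treated at screening with the study product or another collagen dressing. This is an eligibility question only; it should not be read as a reason to withhold or stop a therapy so that a patient qualifies.
2. **Initial Visit CRF 11.3.1:** record the type and last-use date of each prior advanced therapy.
3. **Section 8.3.1:** pre-specify that wound-size change in cm² is shown with and without participants who had prior collagen use or recent other active therapy. The sponsor should define recent, and which therapies count as active, before the first enrolment.

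If the sponsor wants a real-world population, item 1 can be left out; items 2 and 3 then let the reader see how much the result depends on these wounds.

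The cost is a few clinic patients who may become ineligible (none under the alternative), one form question, one date field and one extra table. With 20 participants the reduced set may be small, so the comparison should be read descriptively.

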5.3. Strategies for Recruitment and Retention

The Principal Investigator (PI) maintains an outpatient podiatry clinic. The PI and/or site staff will offer enrollment to patients that may meet the inclusion/exclusion criteria. Participants will be provided with reminder notifications and documentation detailing their scheduled visits to the site.

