6. STUDY PROCEDURES AND ASSESSMENTS

6.1. Day -1 – Pre-screening

Interested potential participants who contact the research site will undergo a brief pre-screening questionnaire via phone to determine initial eligibility. Potential participants will be assigned a screening number in order to de-identify the information on the form. The pre-screening form can be found in Appendix 11.2.1.

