6.2.2. Screening

After obtaining informed consent, research staff will assess eligibility to participate in the study using the screening form provided in Appendix 11.2.2. Participants who qualify will be assigned a subject number. In the event the potential subject has not had a measurement to determine adequate blood flow in the past three months, the PI or research staff will assess blood flow via a handheld vascular Doppler device. Subjects must meet the Doppler criteria mentioned in section 5.1 of this protocol to be randomized

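### Section 5.3 does not require consecutive enrolment and no log of clinic patients passed over is described, so selection into the 20-patient estimate is possible and its size could not be judged

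*Combined protocol and SAP*

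**What the plan says.** Section 5.3 states that "The PI and/or site staff will offer enrollment to patients that may meet the inclusion/exclusion criteria". It does not say that all, or consecutive, patients are to be approached, and no other section available to this review says so.

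Two forms record people who do not enter the study:

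- **Pre-screening form (6.1, Appendix 11.2.1).** Section 6.1 says "Interested potential participants who contact the research site will undergo a brief pre-screening questionnaire via phone". Note 1 to the Schedule of Activities (1.2) limits this step in the same way: "For participants contacting the research facility".
- **Screening form (6.2.2, Appendix 11.2.2).** "After obtaining informed consent, research staff will assess eligibility to participate in the study using the screening form".

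Both forms ask for a reason when someone is dismissed. One exclusion in 5.2 rests on judgement: "Inability, in the opinion of the Investigator to follow protocol requirements, attend follow up visits in a timely manner".

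On design and purpose, 4.1 says "This is a prospective, open-label, case series investigating if a currently marketed collagen dressing can result in improved healing". Section 8.1 says that "a formal power analysis was not conducted" and that "a sample of 20 participants was chosen to provide an initial estimate of product performance in a clinical setting". It adds that the data may feed the power calculation of a larger trial. Section 8.3.1 plans a 95% confidence interval for the mean change in wound size.

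**The concern.** With no comparator, the main result is a mean change in the patients who happened to enter, and what it says about other patients depends on how they entered. If staff tend, even without meaning to, to approach those they expect to do well, the mean moves in the product's favour. The confidence interval does not reflect this, because it measures sampling variation only.

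A log of eligible patients would let a reader see how many were passed over and why. Without one, a series that took nearly every eligible patient and a series that took the most promising few look the same in the report. Three uses of the result are affected: the performance estimate in 8.1, the planning of a later trial, and the question in 2.1 whether this dressing does as well as the bovine collagen dressing in an earlier 20-patient series.

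**Working it through.** **Step 1: who leaves a record.** Setting 5.3, 6.1, 6.2.2 and the two forms side by side:

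- Person who contacts the site and is dismissed: pre-screening form, with reason.
- Person who consents and fails screening: screening form, with reason.
- Clinic patient who is approached and declines before consent: no form described.
- Clinic patient who appears eligible and is not approached: no form described.

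The last two groups are the ones needed to judge selection among clinic patients.

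**Step 2: is there a plan figure to reproduce?** No. The 20 is a stated choice, with no alpha, power, effect size or SD behind it.

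**Step 3: precision at n = 20.** In units of the SD of wound-size change, the 95% half-width is t(0.975, 19) / √20 = 2.093 / 4.472 = 0.468.

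**Step 4: possible shift.** Suppose the fraction f of eligible patients with the best expected prognosis is approached, and that expectation correlates r with reduction in wound size. With normal variables, the shift in the mean is

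shift = r × φ(c) / f, where c is the normal cut-off for the top fraction f.

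The documents give neither f nor r, so both are assumptions. The factor φ(c)/f is 0.350 for f = 0.80 and 0.798 for f = 0.50. For example, with f = 0.50 and r = 0.5, the shift is 0.5 × 0.798 = 0.399 SD, and 0.399 / 0.468 = 0.85 of the half-width. Coverage is the share of 20,000 simulated samples of 20 whose 95% interval contained the mean of all eligible patients.

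| f | r | Shift (SD) | Share of half-width | Coverage |
|---|---|---|---|---|
| 0.80 | 0.2 | 0.070 | 0.15 | 94% |
| 0.80 | 0.3 | 0.105 | 0.22 | 93% |
| 0.80 | 0.5 | 0.175 | 0.37 | 88% |
| 0.50 | 0.2 | 0.160 | 0.34 | 89% |
| 0.50 | 0.3 | 0.239 | 0.51 | 82% |
| 0.50 | 0.5 | 0.399 | 0.85 | 55% |

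As a more extreme case, f = 0.25 gives shifts of 0.254, 0.381 and 0.636 SD for the same three values of r. The last exceeds the half-width.

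**The case against.** The strongest reply is that this is an observational case series that promises only an initial estimate. Without a control arm it cannot separate product effect from natural course or standard care, however patients enter. Baseline wound type, duration and prior treatments are collected (6.3.1), so case mix can be described. Much of the restriction to clean wounds and compliant patients is declared openly in 5.1, in 5.2 and in the 75% dressing-change rule of 8.2, and consecutive enrolment would remove none of it. All this is true. It limits what the change can achieve, but a description of those who enrolled does not show who was left out.

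Some stronger readings are tempting and do not hold:

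- **That enrolment is at the investigator's discretion.** The protocol does not say so. Section 5.3 says that the offer will be made, includes site staff as well as the PI, and is silent on completeness. Some people also contact the site themselves.
- **That choosing small wounds would flatter the product.** Size is recorded in cm² (6.3.2), and 8.3.1 does not specify percent change. A small wound has little area to lose, so choosing such wounds would tend to lower the absolute reduction.
- **That the bias can be put at a number of percentage points of area reduction.** That needs an assumed SD on a scale the plan does not name, besides assumed f and r.
- **That the slow pace of recruitment shows room to choose.** The planned duration and the 20 patients imply a required pace, but the documents give no number of eligible patients seen.

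One caveat remains: a stretch of text between 8.3.3 and 9.2 was not available to this review, so a log described there cannot be ruled out.

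**Conclusion.** The concern holds in a limited form. Consecutive enrolment is not required, and no available section describes a record of clinic patients who are not approached or who decline before consent. Selection towards patients expected to do well is therefore possible, and a reader could not detect or size it. A reader might infer that it will occur; the documents do not show that.

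The size is unknown. Over the main assumed range it runs from 0.07 SD, which hardly matters, to 0.40 SD, which is most of the 0.47 SD half-width. These figures rest on normality and on assumed values of f and r, with r referring to reduction on the plan's cm² scale. They illustrate the possible scale and do not estimate what this trial will do. The point merits a change because the remedy is cheap and the missing record cannot reliably be rebuilt afterwards.

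**What to change.** Three changes:

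1. Reword 5.3 so that enrolment is offered to every consecutive clinic patient who appears to meet 5.1 and 5.2, until 20 are enrolled. The word *appears* is needed because the circulation criterion may be checked by Doppler only after consent (6.2.2).
2. From the first patient, keep a de-identified log, one line per patient, drawn only from routine-care information: appears eligible, approached, declined, enrolled, and the reason if not enrolled. Have the IRB approve it, because 6.2.1 requires written consent before other research activities. Section 6.1 already gives callers a de-identified screening number, so the step is small.
3. Report those counts with the results.

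The cost is a few minutes per patient for existing staff, IRB review of the log, and a possibly less favourable estimate. No treatment or study visit changes. If consecutive enrolment proves unworkable, the report should say so and still give the counts.
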